#### **12.2.4 Serious Adverse Event (SAE)**

An adverse event or suspected adverse reaction is considered “serious” if, in the view of either the investigator or DAIT/NIAID, it results in any of the following outcomes (21 CFR 312.32(a)):

1. Death.
2. A life-threatening event: An AE or SAR is considered “life-threatening” if, in the view of either the investigator or DAIT/NIAID, its occurrence places the subject at immediate risk of death. It does not include an AE or SAR that, had it occurred in a more severe form, might have caused death.
3. Inpatient hospitalization or prolongation of existing hospitalization.
4. Persistent or significant incapacity or substantial disruption of the ability to conduct normal life functions.
5. Congenital anomaly or birth defect.
6. Important medical events that may not result in death, be life threatening, or require hospitalization may be considered serious when, based upon appropriate medical judgment, they may jeopardize the subject and may require medical or surgical intervention to prevent one of the outcomes listed above.

Elective hospitalizations or hospital admissions for the purpose of conduct of protocol mandated procedures are not to be reported as an SAE unless hospitalization is prolonged due to complications.

### **12.3 Grading and Attribution of Adverse Events**

#### **12.3.1 Grading Criteria**

The study site will grade the severity of adverse events experienced by the study subjects according to the criteria set forth in the National Cancer Institute’s Common Terminology Criteria for Adverse Events (CTCAE) [version 5.0]. This document (referred to herein as the NCI-CTCAE manual) provides a common language to describe levels of severity, to analyze and interpret data, and to articulate the clinical significance of all adverse

events. The NCI-CTCAE has been reviewed by the Principal Investigator and has been deemed appropriate for the subject population to be studied in this protocol.

Adverse events will be graded on a scale from 1 to 5 according to the following standards in the NCI-CTCAE manual:

- Grade 1 = mild adverse event.
- Grade 2 = moderate adverse event.
- Grade 3 = severe and undesirable adverse event.
- Grade 4 = life-threatening or disabling adverse event.
- Grade 5 = death.

Events grade 2 or higher will be recorded on the appropriate AE case report form [paper CRF] for this study.

For grading an abnormal value or result of a clinical or laboratory evaluation (including, but not limited to, a radiograph, an ultrasound, an electrocardiogram etc.), a treatment-emergent adverse event is defined as an increase in grade from baseline or from the last post-baseline value that doesn't meet grading criteria. Changes in grade from screening to baseline will also be recorded as adverse events, but are not treatment-emergent. If a specific event or result from a given clinical or laboratory evaluation is not noted above in section 12.2.1 and is also not included in the NCI-CTCAE manual, then an abnormal result would be considered an adverse event if changes in therapy or monitoring are implemented as a result of the event/result.

### 12.3.2 Attribution Definitions

The relationship, or attribution, of an adverse event to the study therapy regimen or study procedure(s) will initially be determined by the site investigator and recorded on the appropriate AE [paper case report form (AE/SAE paper CRF)]. Final determination of attribution for safety reporting will be determined by DAIT/NIAID. The relationship of an adverse event to study therapy regimen or procedures will be determined using the descriptors and definitions provided in Table 12.3.2.

For additional information and a printable version of the NCI-CTCAE manual, consult the NCI-CTCAE web site:

[https://ctep.cancer.gov/protocoldevelopment/electronic\\_applications/ctc.htm#ctc\\_50](https://ctep.cancer.gov/protocoldevelopment/electronic_applications/ctc.htm#ctc_50)

**Table 12.3.2 Attribution of Adverse Events**

Code	Descriptor	Relationship (to primary investigational product and/or other concurrent mandated study therapy or study procedure)
UNRELATED CATEGORY		
1	Unrelated	The adverse event is clearly not related: there is insufficient evidence to suggest a causal relationship.
RELATED CATEGORIES		
2	Possible	The adverse event has a reasonable possibility to be related; there is evidence to suggest a causal relationship.
3	Definite	The adverse event is clearly related.

## 12.4 Collection and Recording of Adverse Events

### 12.4.1 Collection Period

Adverse events will be collected from the time *of enrollment, until a* subject completes study participation or until 30 days after he/she prematurely withdraws (without withdrawing consent) or is withdrawn from the study.

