## 1.3. Clinical Studies

Approximately 2000 volunteers have been challenged in studies conducted by [name], [name], [name], [name], and our other colleagues at UVA over the last 30 years and no serious complications attributable to the viral infection have been detected. The clinical syndrome associated with experimental infection is well-described. Challenge of volunteers with 100 TCID50 produces infection in 90-95% of susceptible volunteers. Symptoms first appear within 24 hours after inoculation and peak at 48-72 hours after challenge. The clinical syndrome is comparable to that reported in natural colds (52, 53) although in one study with identical definitions for duration, the median duration of illness was 3.5 days in volunteers with experimental colds and 5.5 days in volunteers with natural colds (54). Approximately 1/3rd of RV infections, whether natural or experimental, are asymptomatic. Virus shedding in infected volunteers follows a pattern similar to that of the symptoms. Virus concentrations in nasal lavage fluid, based on titers in culture, generally peak 2-3 days after challenge and then rapidly decrease. Virus can still be recovered by culture in 20% of subjects on day 18 after challenge, but no virus shedding is detected by day 20 (55). To the best of our knowledge, human RV-16 has not been withdrawn from investigation or marketing in any country for any reason related to safety or effectiveness. In our studies, we have observed neutropenia in most of the 29 asthmatic subjects and also 16 controls following inoculation with RV-16 in our experimental challenges, which we believe is in keeping with the recruitment of neutrophils into the airways stimulated by RV. However, except for the possibility of bronchitis, which occurs infrequently in experimental infections, no subject has developed clinically significant bacterial infections in our studies, including bacterial sinusitis. Additionally, no subject in our studies with RV-16 has developed ANC's <1000 cells/mm^3.

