### 3. Study Design

#### 3.1. Description of Study Design

A total of 60 subjects will be enrolled in this open label challenge study over a period of 48-54 months (September 2016 – March 2021). These will include 20 subjects in each of 3 cohorts: healthy controls, allergic rhinitis controls, and asthmatics. At Visit 1 subjects will have baseline assessments of lung function and blood work. Viral inoculation will be performed on day 0 and assessments of cold and allergy symptoms, nasal viral titers, nasal mediators, lung function, and FeNO will be obtained on days 0 and days 1, 2, 3, 4, and 7 post-infection (dpi). In addition, methacholine challenges (days -7 and 4) will be performed. Finally, nasal biopsies will be performed on day 4 to assess extent of viral infection and nature of cell death (apoptosis v. necrosis). Each subject will complete the study at day 14.

Table I: Study Outline\*\*\*

Visit #:	1	2	3	4	5	6	7	8	9
	Day -7	Day 0	Day 1	Day 2	Day 3	Day 4	Day 7	Day 14**	Day 21
Symptom Assessment	X	X	X	X	X	X	X	X	X
Negative CoVID19 screen (afebrile/preserved sense of smell)	X	X	X	X	X	X	X	X	X
Pregnancy Test	X	X				X	X		
Viral antibody serology/CBC	X								
Virus inoculation		X							
Viral titers		X	X	X	X	X	X		
FEV1/ FeNO	X	X	X	X	X	X	X	X	
Nasal Scraping		X	X	X	X	X	X		
Nasal Washes / Sponge		X	X	X	X	X	X		
Nasal Biopsy						X			
Blood for Th immune deviation / AEC	X					X			
Methacholine Challenge	X					X			

\*\*\* If subject is still symptomatic at day 14 they will be contacted at day 21 with the possibility of an unscheduled visit. A Day 21 in-person visit will be scheduled if ANC or ALC falls below 500/ $\mu$ L, and does not return to baseline following the Day 14 blood draw. If disease activity increases after day 7 or other concerns arise either between visits 6 and 7 or after visit 8, participants will be instructed to contact study personnel and may be asked to return to the study site for an "unscheduled" visit.

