### **Study Visit 8 (Day 14) – to occur within a +5 day window (D14 to D19)**

Fourteen (14) days after RV inoculation, subjects will return to complete the ACT questionnaire and to report any adverse events. In addition, a limited physical examination will be performed including chest auscultation and a final assessment of FeNO (asthmatics only)/spirometry will be performed. A repeat CBC & differential (3ml purple top) will be drawn if ANC or ALC fell below 500/ $\mu$ L Day 4. If subject is still symptomatic they will be contacted at day 21 with the possibility of an unscheduled visit.

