### **Study Visit 9 (Day 21)**

The Day 21 visit will only occur for subjects who remain symptomatic at Day 14 or whose ANC or ALC falls below 500/ $\mu$ L at Day 4 without recovery by Day 14. This visit will occur by phone except in cases where a repeat CBC & differential is needed to check ANC and ALC counts. Participants will be asked if they continue to have symptoms, and whether or not they have had any new or worsening symptoms/conditions since Day 14. If either of these questions is answered affirmatively, the PI will be contacted, and an unscheduled visit will be arranged if the PI feels it is warranted.

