## 11. Criteria for Participant and Study Completion and Premature Study Termination

### 11.1. Participant Completion

Individuals will have completed their participation when they have completed all of their scheduled study visits.

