### 12.4.3 Recording Adverse Events

Throughout the study, the investigator will record adverse events and serious adverse events as described previously (Section 12.2, *Definitions*) on the appropriate [paper case report form (AE/SAE paper CRF)] regardless of the relationship to study therapy regimen or study procedure.

Once recorded, an AE/SAE will be followed until it resolves with or without sequelae, or until the end of study participation, or until 30 days after the subject prematurely withdraws (without withdrawing consent)/or is withdrawn from the study, whichever occurs first.

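### Adverse-event collection stops at Day 14–19 for most completers but nominally runs to 30 days after withdrawal for others, and completers who are well at Day 14 have no later scheduled inquiry

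*Combined protocol and SAP*

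**What the plan says.** **Collection.** Section 12.4.1 starts adverse-event (AE) collection at enrollment and continues it until a "subject completes study participation or until 30 days after he/she prematurely withdraws (without withdrawing consent) or is withdrawn from the study".

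**Completion.** Section 3.1 states: "Each subject will complete the study at day 14". Section 11.1 states: "Individuals will have completed their participation when they have completed all of their scheduled study visits". Visit 8 may fall anywhere from Day 14 to Day 19 (its own heading and section 8.4).

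**After Day 14.** The Visit 9 text says: "The Day 21 visit will only occur for subjects who remain symptomatic at Day 14", or for those whose neutrophil or lymphocyte count fell below 500/µL on Day 4 and had not recovered by Day 14. Section 8.3 tells participants to get in touch if concerns arise after Visit 8. Unscheduled visits record adverse events.

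**Events already recorded.** Under section 12.4.3 an event is "followed until it resolves with or without sequelae, or until the end of study participation", or until 30 days after withdrawal, and the earliest of these applies.

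**Withdrawn subjects.** Section 11.4 describes one contact, a Day 14 visit that the subject may be asked to complete.

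**Severe exacerbations.** Appendix 1 has the study team available for 30 days after oral steroids, an emergency visit or a hospital admission.

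**Late shedding.** Section 1.3 says: "Virus can still be recovered by culture in 20% of subjects on day 18 after challenge". The same sentence adds that none is detected by Day 20.

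**The concern.** This is a live-virus challenge that includes asthmatics, so the AE record is the main safety output. Section 12.2.3 lists bacterial sinusitis, bronchitis and severe wheezing as infrequent but expected. If one of these begins after Visit 8 in a subject who was well at Day 14, no scheduled question picks it up. It is also unclear whether a volunteered report would fall inside the collection period. The study stopping rules in 11.5 can be met by a single event, so one unreported case could matter.

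The end-of-participation cut-off in 12.4.3 is a separate gap. It applies to serious events as well as minor ones, so a serious event still unresolved at the last visit can leave AE follow-up in a subject who was never withdrawn.

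**Working it through.** The plan gives no figure for this point, so the check is day arithmetic and a comparison of sections.

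**1. Nominal end of AE collection, in days after inoculation**

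Completer: Day 14, or up to Day 19 with the Visit 8 window. Day 21 is possible for the subset contacted then, if that contact counts as participation. Withdrawn subject: withdrawal day + 30.

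| Withdrawal day | Collection to | Beyond Day 14 | Beyond Day 19 | Beyond Day 21 |
|---|---|---|---|---|
| 0 | Day 30 | 16 | 11 | 9 |
| 4 | Day 34 | 20 | 15 | 13 |
| 7 | Day 37 | 23 | 18 | 16 |
| 13 | Day 43 | 29 | 24 | 22 |

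For a Day 4 withdrawal the ratio of windows is 34/19 = 1.8 to 34/14 = 2.4.

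**2. Scheduled inquiry, as opposed to nominal window**

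- Completer, symptomatic or with unrecovered counts at Day 14: contact at Day 21.
- Completer, well at Day 14: nothing scheduled after Visit 8.
- Withdrawn subject: an optional Day 14 visit and nothing near withdrawal + 30 days.

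The longer window is therefore a rule without a matching contact, and the difference in actual ascertainment is smaller than the table suggests.

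**3. Late shedding**

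If the 20% in section 1.3 applied to all 60 subjects, 0.20 × 60 = 12 would be culture-positive on Day 18. With the 90–95% infection rate in section 5.1, and the 20% taken among infected subjects, the figure is 0.20 × 60 × 0.90 = 10.8 to 0.20 × 60 × 0.95 = 11.4. This counts shedding, not adverse events.

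**4. What the earlier challenge study shows**

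Section 1.3 gives cumulative lower respiratory scores by Day 4 and by Day 21. The share added after Day 4 is (Day 21 − Day 4)/Day 21:

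- High IgE: (13.5 − 4.2)/13.5 = 69%
- Low IgE: (8.5 − 1.0)/8.5 = 88%
- Control: (0.7 − 0.4)/0.7 = 43%

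A cumulative score cannot fall, and nothing is reported separately for Days 14–21. These figures place symptoms after Day 4. They do not place them after Day 14.

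**5. Consistency of the end date**

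Participation ends at Day 14 (3.1), at the last scheduled visit (11.1, so up to Day 19), or possibly at Day 21 (Visit 9). The synopsis gives 8–12 weeks per participant. The longest span in the visit schedule, Day −28 to Day 21, is 49 days, or 7 weeks. Section 12.4.1 does not say which of these closes the window.

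**6. Unresolved serious events**

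Appendix 1 offers 30 days of follow-up after oral steroids, an emergency visit or an admission. Section 12.4.3 stops at end of participation for anyone not withdrawn. Section 11.2 makes a severe exacerbation needing emergency care, admission or systemic steroids a ground for withdrawal, so the Appendix 1 group largely overlaps with subjects who already have the longer window. Treated pneumonia is a study stopping event in 11.5 but is not named in 11.2. Such a subject would be withdrawn only through the investigator-judgement items.

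**The case against.** The strongest reply is that the plan already covers the likely late events. Those still symptomatic at Day 14 are called at Day 21. Section 8.3 gives everyone a route back after Visit 8, and section 12.4.2 accepts unsolicited complaints as a source. Severe exacerbations have 30 days of follow-up through Appendix 1 or through withdrawal. Section 1.3 gives peak symptoms at 48–72 hours and a median illness of 3.5 days. Section 5.1 argues that long-term effects could hardly be told apart from later natural colds.

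Much of this stands, and it rules out three stronger readings.

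- **Late events are missed in most subjects.** Routine inquiry ends early for completers who are well at Day 14, but the documents give no late-event rate, and volunteered reports remain possible.
- **Virus and symptoms persist to Days 18–21.** The sentence reporting 20% on Day 18 also reports no shedding by Day 20. The 21-day scores do not isolate any period after Day 14.
- **Unequal windows bias a comparison of cohorts.** Section 13 plans no between-cohort analysis of adverse events, and the DSMB receives listings. Most withdrawal criteria in 11.2 apply to all three cohorts, and no withdrawal rate is given.

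The reply does not close the gap. Contact after Visit 8 depends on the subject, and the text does not place it inside the 12.4.1 period. The Appendix 1 provision sits under exacerbation treatment and mostly serves subjects whom 11.2 would withdraw anyway. The section 5.1 argument concerns long-term effects, not the weeks just after Day 14.

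**Conclusion.** The point holds as a moderate gap in safety ascertainment. As written, collection and follow-up stop at Day 14–19 for most completers, and possibly at Day 21 for the subset contacted then. For subjects withdrawn between Day 0 and Day 13 they nominally run to Day 30–43, with no contact to support it. Completers who are well at Day 14, with no unrecovered cytopenia, have no later scheduled inquiry. An unresolved serious event in a completer can drop out of AE follow-up at end of participation, and sections 12.4.3 and Appendix 1 need to be reconciled on this.

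The size is known in days, not in events. The figure of about 11–12 subjects shedding on Day 18 assumes that the 20% in section 1.3 carries over to this study. A reader might infer that symptoms last to Day 21 or that a material number of events would be lost, but the documents support neither. Sample size, type I error and the primary analyses are unaffected.

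**What to change.** 1. In 12.4.1, state one AE end date, counted from inoculation, for every inoculated subject, and close it with a defined contact. Making the existing Day 21 telephone contact universal is one way, and it covers the period in which shedding is reported to end. If the 30 days after withdrawal is kept as an addition, define in 11.4 the contact that goes with it.
2. State that the Day 21 contact and unscheduled contacts fall inside the collection period. Align 3.1, 11.1 and the 8–12 weeks in the synopsis with the chosen date.
3. In 12.4.3, follow unresolved serious and related events to resolution or stabilisation instead of stopping at end of participation, and reconcile the text with the 30-day follow-up in Appendix 1.

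The cost is protocol wording and at most 60 short calls for the 60 planned subjects, some of which the current Day 21 rule already requires. Any inoculated subject who is withdrawn and replaced under 11.3 would add one call.

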### 12.4.2 Collecting Adverse Events

Adverse events (including SAEs) may be discovered through any of these methods:

- Observing the subject.
- Interviewing the subject [e.g., using a checklist, structured questioning, diary, etc.].
- Receiving an unsolicited complaint from the subject.
- In addition, an abnormal value or result from a clinical or laboratory evaluation can also indicate an adverse event, as defined in Section 12.3, Grading and Attribution of Adverse Events.

### 12.4.3 Recording Adverse Events

Throughout the study, the investigator will record adverse events and serious adverse events as described previously (Section 12.2, *Definitions*) on the appropriate [paper case report form (AE/SAE paper CRF)] regardless of the relationship to study therapy regimen or study procedure.

Once recorded, an AE/SAE will be followed until it resolves with or without sequelae, or until the end of study participation, or until 30 days after the subject prematurely withdraws (without withdrawing consent)/or is withdrawn from the study, whichever occurs first.

## 12.5 Reporting of Serious Adverse Events and Adverse Events

### 12.5.1 Reporting of Serious Adverse Events to IND Sponsor and to DAIT/NIAID

This section describes the responsibilities of the site investigator to report serious adverse events to the IND sponsor and to DAIT/NIAID. Timely reporting of adverse events is required by 21 CFR and ICH E6 guidelines.

The Site investigator will report all serious adverse events (see Section 12.2.3, Serious Adverse Event), regardless of relationship or expectedness within 24 hours of discovering the event.

For serious adverse events, all requested information on the AE/SAE [paper CRF] will be provided. However, unavailable details of the event will not delay submission of the known information. As additional details become available, the AE/SAE [paper CRF] will be updated and submitted.

Reporting to the IND Sponsor:

[name]  
Department of Medicine  
[name]  
University of Virginia Health System [name]  
[contact]  
[[contact]](mailto:[contact])

**12.5.2 Reporting to Health Authority**

After an adverse event requiring 24 hour reporting (per Section 12.5.1, *Reporting of Serious Adverse Events to Sponsor*) is submitted by the site investigator and assessed by DAIT/NIAID, there are two options for DAIT/NIAID to report the adverse event to the appropriate health authorities:

**12.5.2.1 Annual Reporting**

The IND Sponsor will include in the annual study report to health authorities all adverse events classified as:

- Serious, expected, suspected adverse reactions (see Section 12.2.2, *Suspected Adverse Reaction*, and Section 12.2.3, *Unexpected Adverse Event*).
- Serious and not a suspected adverse reaction (see Section 12.2.2, *Suspected Adverse Reaction*).
- Pregnancies.

Note that all adverse events (not just those requiring 24-hour reporting) will be reported in the Annual IND Report.

**12.5.2.2 Expedited Safety Reporting**

This option, with 2 possible categories, applies if the adverse event is classified as one of the following:

**Category 1: Serious and unexpected suspected adverse reaction [SUSAR]** (see Section 12.2.1.1, *Suspected Adverse Reaction* and Section 12.2, *Unexpected Adverse Event* and 21 CFR 312.32(c)(1)i).

The IND sponsor shall report any suspected adverse reaction that is both serious and unexpected. The IND sponsor must report an adverse event as a suspected adverse reaction only if there is evidence to suggest a causal relationship between the study drug and the adverse event, such as:

1. A single occurrence of an event that is uncommon and known to be strongly associated with drug exposure (e.g., angioedema, hepatic injury, or Stevens-Johnson Syndrome);
2. One or more occurrences of an event that is not commonly associated with drug exposure, but is otherwise uncommon in the population exposed to the drug (e.g., tendon rupture);
3. An aggregate analysis of specific events observed in a clinical trial (such as known consequences of the underlying disease or condition under investigation or other events that commonly occur in the study population independent of drug therapy) that indicates those events occur more frequently in the drug treatment group than in a concurrent or historical control group.

